#### *Oculomotor Measures*

Oculomotor control performance will also be compared using a 3 x 2 mixed-model ANOVA for each of the dependent variables. For smooth pursuit tracking performance, mean eye peak velocity and tracking lag will be submitted to separate 3 (group) x 2 (session) x 2 (random vs. sinusoidal task condition) mixed-model ANOVA.

### **(10) FACILITIES AND PERFORMANCE SITES:**

All MRI scanning will be performed on a 3 Tesla Philips Achieva MRI scanner located in Imaging Research Center (IRC) in the Cincinnati Children’s Hospital Research Foundation (CCHRf). Sedation will not be used for any of the test visits. The entire MRI series, including anatomical imaging, 3d T1, DTI, rs-fMRI, SWI, and HARDI will be completed in 60 minutes or less (see Table 1. below for detailed specifications).

**(11) POTENTIAL BENEFITS:**

Participants of this study will not receive any direct or immediate benefits by completing this study. However, they will be contributing to research involving the potential for major contributions to future TBI/concussion prevention strategies.

**(12) POTENTIAL RISKS, DISCOMFORTS, INCONVENIENCES AND PRECAUTIONS:**

The Device partially circumnavigates and compresses the neck in the same way that a compression garment (non-medical apparel) behaves, and very similar to the compression exerted by a necktie (although this device is open over the trachea and can be pulled off if inadvertently gripped). These garments have been shown to gently facilitate natural response mechanisms in several small neck muscles and tendons (the Omohyoids), which are universally present in mammals and birds.

The physiologies imparted by these Omohyoids (and further facilitated by these garments) merely approximate natural physiologies, which occur when individuals lie in the prone, or supine position, and are also comparable to the simple act of yawning (which has been shown to collapse the jugulars). The Device will intentionally deliver an exacting, but gentle compression to the Omohyoid muscles in the neck allowing these muscles to optimize blood outflow of the neck vasculature. In the upright position (without the collar), the resultant vascular blood column siphons volume out of the neck, rapidly, creating a negative pressure on the cranium and resulting in a slight “under filling” and “sloshability” inside the skull. The Omohyoid muscle raises the volume of the intracranial space by design. The Device does not contain any inherently rigid structures in its design. Similarly, neckties circumnavigate the neck, and safely raise intracranial pressure and volume comparable to the Device. The Device is manufactured of a soft rubber similar material and should be barely noticeable to the wearer. Careful MRI studies have confirmed an increase in blood volume in the brain but have also shown that there is no significant change in brain blood flow pattern with wearing a “tight necktie” (Rafferty, Quinn et al. 2010).

Although the venous jugular flow beneath the pressure cuff may be temporarily halted or slowed, the venous outflow from the cranium is never completely stopped, particularly from the anastomosis between the spinal vein and the basilar plexus and occipital sinuses *which are incompressible.*”(Gregg and Shipley 1944) Jugular compression has few known physiological effects besides the intended increase in cerebral blood volume and pressure. Only one innocuous physiology has ever been shown to alter with jugular compression. “Previous studies have shown that the decline in urinary sodium excretion which occurs normally in the sitting position, as compared with recumbency, can be partially but not completely prevented by compression of the neck (Lewis, Buie et al. 1950, Torres and Ellington 1970). This decline in urinary sodium excretion is minimal. There was no correlation between EEG changes and changes in systolic blood pressure occurring during

jugular or carotid compression(Torres and Ellington 1970). Further, studies on complete resection of the IJV note that, “the clinical observation that bilateral resection of the IJV is usually well tolerated suggests the presence of alternative, non-jugular pathways.”(Gius and Grier 1950)

*Effect of Body Position and Exercise on ICP:* “At rest, compared with the reference 30-degree head-up position, the supine position increased intracranial pressure (ICP) by 6.21 mm Hg (35% with  $P<.01$ ).”(Brimioulle, Moraine et al. 1997) Restated, just lying down increases ICP more than the Device (6.21mm Hg = 35% rise versus this device at only 25%).  
*Valsalva and raising ICP:* We define Valsalva, where a person tries to exhale forcibly with a closed glottis (windpipe), so that no air goes out through the mouth or nose. “When the Valsalva maneuver was performed during resistance exercise, the ICP rose to 31 mmHg (a rise of 138%). No complications were associated with participating in this investigation.”(Haykowsky, Eves et al. 2003) In other words, the Device facilitates the intended actions of the omohyoid with less pressure than the act of lying down or performing the Valsalva (holding one’s breath and bearing down, which would be expected to occur regularly on a playing field).

Instead of letting three to five milliliters of blood rapidly flow out of one’s brain upon standing, the Device will serve to retain that fluid inside the skull where it is believed to cushion the brain from external energy impacts and concussions. In rats, this simple action prevented 83% of TBI indicators during two 900 G impact studies at the West Virginia University.(Smith, Bailes et al. 2012, Turner, Naser et al. 2012)Considering the above mentioned findings on jugular compression, this device can be considered not to meet the definition of a “significant risk device,” as that term is defined in 21 C.F.R. § 812.3(m).

**MR Imaging of the Brain:** The risk the magnetic fields and the strengths, and radio waves is vanishingly small. Some patients can experience anxiety from the confined space of the magnet’s bore. Therefore people with known claustrophobic tendencies may be excluded from the study. Another minor concern when using magnetic resonance technology is the noise the magnet makes when collecting data. Noise abatement measures are used; headphones and music with a selection of music options. Ferrous implants and or piercings can be affected in the magnetic field. Therefore participants will be advised to remove these and or scanned with a metal detector to screen for such objects.

Our colleague’s previous experience with MRI experiments (who will be present and has a decade of experience with this technology) has provided confidence that there should be no psychological, physical, legal, or social risks involved with MRI experiments in general, though participants may be anxious about the scan, possibly causing them slight stress. The MRI scanning will be performed using the 3 T Siemens Trio MRI scanner. MRI does not involve ionizing radiation and scans up to 8 T are considered as non-significant risk. The risks common to all MRI scans can be described as: (1) ferromagnetic objects introduced into the magnetic field, (2) confinement in the scanner bore, (3) radio-frequency (RF) heat deposition in tissue which is monitored by the system to conform with FDA guidelines, and (4) acoustic noise. These risks are addressed below: Participants are allowed to communicate with the MR operator via an always-on, two-way intercom at any time. In addition, the

participants have a hand-held air ball to squeeze in the event that they elect to be removed from the magnet immediately. Thus, the participants have control over their presence in the magnet, which in turn tends to minimize feelings of claustrophobia.

The MR imaging will be initially reviewed by a licensed radiologist just as it would be if it were being used as part of routine medical care. There is a possibility that while reviewing MR images we may see an abnormality that we did not expect to see in this study. In this event, we will notify the participant's legal representative (or participant is 18 years or older) if we see such an incidental finding. Depending on the type of incidental finding, we may contact the participant by mail or by phone. A member of the research team will discuss the incidental finding with the legal representative (or participant if over the age of 18 years). If the participant chooses, we will give information about this incidental finding to their primary doctor or we will refer them to an appropriate doctor for further evaluation. The costs for any care that will be needed to diagnose or treat an incidental finding would not be paid for by this research study.

**Data Storage.** There is also a minimal risk that the data collected for each participant may be viewed by individuals outside the research team. The risk that confidential data may be viewed is relevant for both the written forms and electronic databases. Precautions, such as password-protected computers, locked cabinets and coded identification numbers, are in place to minimize this risk.

**Adverse Events.** During the course of the investigation, injuries consistent with the sports being monitored are expected to occur (E.g. concussion, musculoskeletal injury, bone fractures). Care of all injuries will follow standard of care as directed by the team's athletic trainer and/or the participants treating physician. CCHMC will not be responsible for the medical treatment of any injuries that are not directly related to wear of the Q-collar device. In the case of an adverse event that is determined to be directly related to the wear of the Q-collar during competitive play, the principal investigator will report such event to Cincinnati Children's Hospital Medical Center IRB as any future funding organizations in a manner consistent with the requirements of each organization. As described in the consent, if a participant believes they have sustained an injury as a result of the study then they are instructed to contact the principal investigator or director of social services who in turn will then contact CCHMC IRB and necessary funding institutions, as aforementioned. If a participant sustains an injury during testing they will be referred to the most appropriate medical facility or seek medical attention by the physician/medical specialist of their choice.

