### **Injury Surveillance**

*Device and Compliance Acceptance:* The study coordinator will be responsible for providing the appropriate intervention (device or no-device) to each team based on their assignment prior to the season onset. At first fitting of the collar a registered vascular technologist will utilize ultrasound to ensure that the collar fits correctly and is activated as prescribed. Following the initial fitting, each athlete will receive adequate instruction on how to properly use the device on a daily basis. Throughout the season, the coordinator will make routine visits to each team to monitor the proper usage and fitting of the device, tracking the use of the device by each athlete individually. At the end of practice/game the device will be collected by the athletic trainer and/or stored in the athlete's locked locker. The device is NOT to go home with the athlete.

*New Concussion Surveillance and Follow-up:* Each participant will be provided with an X Patch accelerometer (X2 Biosystems; Seattle, Washington) The X patch adheres to the head, just behind the ear using an adhesive patch, as seen in the image below. .

X2 is a small and durable device that is attached to the back of the neck behind the ear to track impacts, and it stores data for uploading to a PC. This X2 accelerometer accurately measures the severity of impacts by converting data such as high impact collision into usable data outputs. X2 data will be used in final analysis to normalize the exposures to potential concussive events. All impacts of greater than 10 g-force will be recorded and utilized in the post-season analyses. No one besides those approved by this IRB protocol will have access to any data. If available, video of games and practices will be used to validate and confirm head impacts recorded by accelerometers.

concussion testing completed as part of the study, will be used in making any clinical decisions for return to play.

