### **(13) RISK/BENEFIT ANALYSIS:**

Participants will be approached for participation via the appropriate method. The purpose and the study protocol will be fully explained in conversation and with the informed consent process.

On the day of the study, the investigators will confirm that the volunteer participant has no health impairment as outlined in the exclusion criteria. Time will be taken to repeat the aims of the study, test protocol, and to answer any remaining questions posed by the participant.

The methods described in this protocol have been used extensively in previous testing in the laboratory. During previous testing, there have been no reported injuries, adverse events or complications. Additionally, the investigators have considered potential risk for injury and have taken additional steps, described in the protocol, to minimize these risks.

Subject participation will be halted should an adverse event while wearing the collar, such as syncope, occur. Any adverse events will be immediately reported. The safety officer will evaluate all adverse events and will determine if early stopping of the study due to safety concerns is warranted. Given the study design and sample, we do not deem futility or efficacy stopping rules are warranted.

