[name], Division of Sports Medicine, will serve as a study monitor for this project, while the PI and study coordinators will be responsible for monitoring data quality and adverse events. The monitor will review adverse events and unanticipated events at the time they occur and will report his assessment of the event(s) to the PI.

This research study involves only minimal risk for participants (see Risk/Benefit Analysis section (15)). Further assurances regarding participant safety and protection of private and confidential participant information have been outlined in the Potential Risks, Discomforts, Inconveniences and Precautions section (14), the Privacy section (18) and the Confidentiality section (19). If during the, preliminary analyses the research team identifies strong evidence of harm from the Q-collar device the study will be stopped immediately.

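### The Section 12 trigger for reporting adverse events to the IRB is narrower than the Section 13 rule, and no section assures a comparison of harm by arm

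*Combined protocol and SAP*

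**What the plan says.** The Adverse Events paragraph of Section 12 begins by noting that "injuries consistent with the sports being monitored are expected to occur", and leaves their care to the athletic trainer or treating physician. It then gives two routes to the IRB and funding bodies. The first starts "In the case of an adverse event that is determined to be directly related to the wear of the Q-collar during competitive play"; in that case "the principal investigator will report such event to" those bodies. The second applies "if a participant believes they have sustained an injury as a result of the study", and runs through the principal investigator or the director of social services.

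Section 13 is worded more broadly: "Any adverse events will be immediately reported. The safety officer will evaluate all adverse events". It also leaves to the safety officer whether safety concerns justify stopping early.

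Section 14 makes the safety officer the contact for severe events, without defining severe. It makes the investigator and coordinators responsible for monitoring adverse events, and it has a study monitor review adverse and unanticipated events as they arise. It ends with a stop for harm: "If during the, preliminary analyses the research team identifies strong evidence of harm from the Q-collar device the study will be stopped immediately".

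On where the collar is worn, Injury Surveillance in Section 8 says: "At the end of practice/game the device will be collected by the athletic trainer".

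**The concern.** The sections give different answers to which events are reported and to whom. A coordinator following Section 12 would send the IRB a narrow, pre-judged set of events. One following Section 13 would report everything, but would not know to whom.

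The narrow trigger also bears on how harm could be detected. Concussions, musculoskeletal injuries and fractures are expected in this population whatever the arm. If the collar raised the rate of such injuries, no single case would look collar-related; the effect would show only as an excess over the no-collar arm. A relatedness judgement applied before recording would remove the events needed to see that excess. The trial has no sham, and Sections 8 and 14 give the coordinators both the handing out of assignments and the monitoring of adverse events, so event capture could differ with knowledge of arm.

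**Working it through.** No arithmetic applies: the documents give no adverse event rate, safety effect size or power figure. The check sets the provisions side by side.

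| Provision | Events covered | Who acts | Recipient | Limit stated |
|---|---|---|---|---|
| Section 12, first route | Adverse events | Principal investigator | IRB and funders | Directly collar-related; competitive play |
| Section 12, second route | Injury the participant attributes to the study | Participant, through the investigator or director of social services | IRB and funders | None by arm or setting; depends on the participant's belief |
| Section 13 | Any adverse event | Reporter not stated; safety officer evaluates | Not stated | None |
| Section 14, severe events | Severe adverse events (undefined) | Not stated | Safety officer | Severity only |
| Section 14, monitoring | Adverse and unanticipated events | Investigator and coordinators; study monitor | Principal investigator | None |

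1. *Scope.* The first and third rows differ in which events count, and the third has no recipient. They can be made compatible by treating Section 13 as internal reporting and Section 12 as external notification, but the protocol does not say this.

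2. *Setting.* Section 8 has the collar collected after practices and games alike, so it is worn at both. Read literally, the first route omits a collar-related event at practice. Sections 13 and 14 would still cover it internally.

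3. *Arm.* The comparator in Section 6 wears no device. No event in that arm can be directly related to wearing the collar, so the first route can yield no event there, by definition. This applies to that route alone.

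4. *Recording and analysis.* None of the provisions defines an adverse event, says how events are elicited, or prescribes a common form for both arms. Section 9 names no adverse event outcome and no table of events by arm. Its Poisson model compares intervention with no intervention using a playing-time offset, but does not say which event is counted.

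5. *The stop for harm.* Section 14 refers to preliminary analyses by the research team, while Section 13 gives the judgement on stopping to the safety officer. Neither says what comparison would supply the evidence.

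**The case against.** The strongest reply is that Section 12 governs what is sent to outside bodies, not what is recorded. Notifying the IRB of device-related events while reviewing everything internally is a coherent two-tier system. That stands, and it rules out two stronger conclusions that a reader might draw.

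- *That only collar-related events are ever reported.* The documents do not support this. The second Section 12 route has no limit by collar, arm or setting, so a no-collar participant can use it, and Section 13 speaks of any adverse event.
- *That harm cannot be compared between arms.* This does not follow either. Sections 13 and 14 call for evaluation and monitoring of adverse events without restriction by arm, and concussion has its own surveillance in Section 8.

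Three further points have some force. First, competitive play may mean sport as opposed to laboratory testing, since the same paragraph deals separately with injury during testing, and the football study in Section 3 describes a competitive season that included practices. That makes the phrase ambiguous, which is still a reason to change it. Second, Section 12 does not say who judges relatedness, so an unblinded judgement is a plausible inference and not a stated fact. Third, the surveillance text in Section 8 ends in a broken fragment and the consent pages are not available, so missing detail on recording should be argued with caution.

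What the reply does not supply is a recording rule common to both arms or a summary by arm. The participant route depends on someone suspecting the study, and the safety officer can evaluate only what arrives.

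**Conclusion.** The point holds as a conflict of scope and a gap in the safety plan, and it is worth correcting. The Section 12 trigger is narrower than the Section 13 rule. Taken literally, it drops collar-related practice events from investigator-initiated reporting to the IRB, and it cannot be met in the no-collar arm. Since no section provides uniform recording or tabulation by arm, the evidence that Section 14 would need to act on harm is not assured, although it is not ruled out.

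No numerical size can be given. The practice gap depends on the share of collar wear that falls in practice, which the documents do not state. The conclusion rests on two assumptions: that competitive play is read in its ordinary sense of games, and that the unavailable text contains no common recording rule. If the sponsor means the phrase to include practice, the practice gap closes but the other points remain.

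**What to change.** - Reconcile Sections 12, 13 and 14 so that they state which events are reported, by whom, to whom and how quickly, and define severe.
- Remove the restriction to competitive play, or widen it so that practice is plainly covered.
- Record all adverse events and injuries in both arms on the same form, at practices and games, before anyone judges relatedness. Keep relatedness as a field on the form and not as a filter for entry.
- Add to Section 9 a table of adverse events and injuries by arm with exposure denominators, and supply it to the safety officer. State that this is the summary on which the Section 14 review of harm will draw.

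The cost is an edit to the protocol and a short log kept by trainers and coordinators who, under Section 8, are already in contact with the teams. Playing time is already needed for the Section 9 offset and can serve as a denominator; practice time is listed there as a candidate predictor. The downside is that more routine soccer injuries have to be logged.

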### **(13) RISK/BENEFIT ANALYSIS:**

Participants will be approached for participation via the appropriate method. The purpose and the study protocol will be fully explained in conversation and with the informed consent process.

On the day of the study, the investigators will confirm that the volunteer participant has no health impairment as outlined in the exclusion criteria. Time will be taken to repeat the aims of the study, test protocol, and to answer any remaining questions posed by the participant.

The methods described in this protocol have been used extensively in previous testing in the laboratory. During previous testing, there have been no reported injuries, adverse events or complications. Additionally, the investigators have considered potential risk for injury and have taken additional steps, described in the protocol, to minimize these risks.

Subject participation will be halted should an adverse event while wearing the collar, such as syncope, occur. Any adverse events will be immediately reported. The safety officer will evaluate all adverse events and will determine if early stopping of the study due to safety concerns is warranted. Given the study design and sample, we do not deem futility or efficacy stopping rules are warranted.

